Sasso and colleagues retrospectively reviewed their experience with selective nerve blocks in predicting surgical outcome for lumbar and cervical radiculopathy. The authors reviewed 101 patients all, which underwent cervical or lumbar decompression. The injection technique was standardized for both the cervical and lumbar regions. A positive injection was determined if there was an immediate >95% relief of pain and VAS score of 0-1. The overall predictive value of SNRB was 91% while the negative predictive value was 40%²¹. Williams and Germon recently reported on their experience with SNRB in 100 consecutive patients. This retrospective review included patients who presented with diagnostic uncertainty based on history, physical exam and imaging as to whether nerve root compression was responsible for their symptoms. All patients had imaging demonstration of either foraminal or lateral recess stenosis. All patients underwent a standardized injection performed by the same operator. A standardized approach to a positive or negative injection was utilized. Specifically, the injection to be effective result in 1) initial reproduction of the patient's typical radicular pain, 2) an initial radiculogram, 3) an appropriate motor and sensory disturbance immediately after blockade and 4) and whether good pain relief during activity was present during presence of blockade. In patients who's symptoms did not improve 3 months after surgery, an MRI was ordered. Fifty-one patients underwent decompression surgery after a successful SNRB; 41 patients had a good outcome after surgery, while 10 did not. Nine patients who did not have relief of their pain still underwent decompression surgery; 6 of these patients had relief of their symptoms, 2 did not improve and one was lost to follow-up. The positive predictive value was found to be 80.4%; while the

negative predictive value was 22.2%. The resultant sensitivity was 85.4% and specificity 16.7%²⁶.

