Both Sasso et al. and Williams and Germon studies are limited by their retrospective design. Bias regarding patients chosen for surgery, type of surgery performed and ultimate outcome cannot be minimized or mitigated. Patients included were not homogeneous, especially in Sasso et al, where cervical patients were included. Validated patient reported outcome measures were not utilized, which negatively impacts the true definition of outcome following surgery and overall predictive value of SRNB. Most importantly, the threshold for a positive response was determined and set *a priori* in both studies. A dichotomous positive or negative response to injection was utilized and is likely overly simplistic. As stated by the authors, the threshold for a positive response may have been set too high and this could have explained the low negative predictive value of SNRB reported. Lastly, the sample size in both studies was too small to make subgroup analysis and determine which aspects of the response to the SNRB predict a good surgical outcome.

There is currently no agreed upon gold standard against which to make comparisons of accuracy of SNRB. Some have defined accuracy based on demonstration of epidural spread of contrast along the nerve of interest²⁷, anatomic studies¹⁵, changes in physiology²², or compared to EMG or myelography¹⁰. Moreover, there is no agreed upon standardized needle placement for SNRB. The needle may be placed classically at the superior anterior foramen, alternatively, the needle may be placed in Kambin's triangle. Both target the nerve in the foramen, but at differing anatomic positions. An injection in either place should block the desired nerve, but in differing anatomic locations and potentially resulting in a varying diagnostic response. Many consider a transforaminal epidural steroid injection diagnostic, yet this injection involves epidural placement of drug and steroid and thus is not diagnostic. Lastly, there is no standard as to what medication or cocktail of medication and volume should be injected. Differing volumes and concentration of anesthetic injected will obviously have a variable impact on diagnostic accuracy.

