To improve the diagnostic value of SNRB, a threshold between positive and negative responses will be set that is best able to predict whether a patient will have a good surgical outcome. To measure the response to injection, post-injection VAS pain scores and functional assessments will be compared to pre-injection values for each patient.

First, the functional and VAS pain measures of improvement will be analyzed individually. A positive functional response to injection will be defined by setting thresholds in the timed 30-meter walk test that best differentiates patients who respond to surgery from those who do not. The accuracy of the test will be defined by its sensitivity and specificity and by its negative and positive predictive values. Separately, a threshold defining a positive response to injection will be set using VAS leg pain improvements over pre-injection values.

Then, a logistic regression analysis will be performed, including pain assessments and walk test improvements as predictors. This model will assign a value between 0 and 1 that represents how likely it is that a patient who responds to SNRB with some amount of reduction in leg pain and improvement in

[name]

Threshold Response of Selective Nerve Root Block

functional ability has a good surgical outcome. A threshold in the model's predictive values will be set to define a positive response to the injection. This will again be done to maximize its diagnostic accuracy with respect to sensitivity and specificity and to positive and negative predictive values.

Positive and negative predictive values and their 95% confidence intervals will be reported both for the individual analyses and for the combined logistic regression analysis. Lastly, variable selection will be performed in an attempt to simplify the logistic regression model.

Due to the fact that a threshold response to SNRB has not been studied, we are not able to perform an adequate power analysis. We will use the data from this pilot study to perform a power analysis for a planned larger randomized trial. To have an adequate sample yet complete the study in a 12 month time period we plan to enroll 50 patients.

Plans for Dissemination of Results

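### The combined logistic model and the variable selection after it have no safeguard against overfitting in 50 patients, so predicted probabilities are likely to be too extreme and the selected predictors unstable

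*Combined protocol and SAP*

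**What the plan says.** The Statistical Analysis section first sets separate thresholds for the walk test and for VAS leg pain. It then states that "a logistic regression analysis will be performed, including pain assessments and walk test improvements as predictors". The output is given a direct probability reading: "This model will assign a value between 0 and 1 that represents how likely it is that a patient who responds to SNRB" has a good surgical outcome. Next, "A threshold in the model's predictive values will be set to define a positive response to the injection", and predictive values with 95% confidence intervals are to be reported. The analysis closes with "Lastly, variable selection will be performed in an attempt to simplify the logistic regression model".

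The section names no candidate list, selection algorithm, stopping rule, penalty, shrinkage or internal validation. On sample size it says "we are not able to perform an adequate power analysis" and "To have an adequate sample yet complete the study in a 12 month time period we plan to enroll 50 patients".

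In Background and significance, the protocol criticises the size of two earlier series as a basis for predicting surgical success: "the sample size in both studies was too small to make subgroup analysis and determine which aspects of the response to the SNRB predict".

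**The concern.** Choosing among block-response measures asks which parts of the response predict outcome, and the protocol itself says larger series could not answer that. A logistic model with several correlated predictors and few patients in the smaller outcome group fits noise. Its coefficients are then too large and its probabilities lie too close to 0 and 1. Selection in the same data adds a second problem: the retained set may change from sample to sample.

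Two outputs are at stake. One is the 0-to-1 score, which is to be read as a likelihood and cut at a threshold. The other is any statement about which measures matter. Future Funding and Next Steps says the threshold findings will inform the design of a larger study, so errors in either could carry forward. This is separate from the optimism of choosing a cut-off in the data used to evaluate it, because here the probability scale and the predictor set are themselves affected.

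**Working it through.** **Inputs from the protocol**
- Sample size: 50, set by the timetable. No formula lies behind it, so there is no figure to reproduce.
- Response measures collected (Description of Procedures, items 1 to 4): immediate VAS leg change, post-walk VAS change, walk time, cadence, 48-hour VAS and duration of relief, which makes six. Item 2 adds pain replication and motor/sensory change, giving up to eight. The plan does not say which enter the model.
- Outcome: a four-part definition (item 7). No expected rate is given.
- Only available guide to the rate: the second cited series in Background and significance. It reports 41 good and 10 not good among block-positive patients, and 6 good, 2 not and 1 lost among block-negative patients. Its predictive values reproduce: 41/51 = 80.4% and 2/9 = 22.2%. Overall success is (41 + 6)/(41 + 10 + 6 + 2) = 47/59 = 79.7%.

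**Patients in the smaller outcome group, per candidate**
- 80% success: 50 × 0.20 = 10. With six candidates 10/6 = 1.7; with eight, 10/8 = 1.2.
- 50% success: 25. With six candidates 25/6 = 4.2; with two, 25/2 = 12.5.
- 20% success: 10 again.

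**Measure used.** The calibration slope is the coefficient obtained when outcomes in new patients are regressed on the model's log-odds. Below 1 means too extreme. For scale, with a slope of 0.5 and a calibration intercept of zero, a stated 90% (odds 9) corresponds to true odds of 9^0.5 = 3, or 3/4 = 75%.

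**Simulation A: five correlated candidates.** N = 50, two true predictors, odds ratios 1.6 to 2.0 per SD, success 20, 50 or 80%.
- Full maximum-likelihood model: median slope 0.42 to 0.56.
- After selection: 0.49 to 0.65.
- Exact true pair selected: 3 to 16% of runs.
- Cross-validated ridge on the same five: slope 1.12 to 1.31, with higher AUC and lower Brier score in every scenario.

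**Simulation B: a wider grid.** 600 cohorts per setting (200 for ridge). Backward elimination at p<0.05 / p<0.157. Selected rows, all with correlation 0.4:

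| N | Candidates (true) | OR per SD | Success | Exact set | Slope, full | Slope, selected | Slope, ridge |
|---|---|---|---|---|---|---|---|
| 50 | 6 (2) | 2 | 80% | 4% / 10% | 0.40 | 0.57 / 0.48 | 1.11 |
| 50 | 6 (2) | 2 | 50% | 10% / 19% | 0.51 | 0.65 / 0.59 | 1.01 |
| 50 | 6 (2) | 3 | 50% | 42% / 34% | 0.57 | 0.72 / 0.65 | 1.02 |
| 50 | 8 (2) | 2 | 80% | 4% / 8% | 0.30 | 0.52 / 0.40 | 1.07 |
| 50 | 4 (1) | 3 | 50% | 76% / 57% | 0.64 | 0.81 / 0.72 | 1.02 |
| 50 | 2 (1) | 3 | 50% | 86% / 79% | 0.80 | 0.86 / 0.83 | 1.14 |
| 100 | 6 (2) | 2 | 80% | 22% / 26% | 0.65 | 0.76 / 0.71 | 1.15 |
| 100 | 6 (2) | 2 | 50% | 44% / 38% | 0.74 | 0.82 / 0.78 | 1.15 |

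Across all 14 settings at N = 50, the median slope after selection was 0.40 to 0.86 and never reached 1. The full model gave 0.30 to 0.83 and ridge 0.99 to 1.24. The wrong set was chosen in most runs under both rules in 9 settings, under one rule in 2, and under neither in 3. Doubling N to 100 helps but does not settle the choice, which agrees with the protocol's own remark about the earlier series.

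**The case against.** Several stronger readings are tempting, and the documents do not support them.

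- **The simplified model will usually hold the wrong predictors.** This depends on the number of candidates, the effect sizes and the outcome rate, none of which the plan gives. It failed in the three settings with two to four candidates, an odds ratio of 3 and balanced outcomes. Recovery of the exact set is also a severe test: in runs of the five-candidate design, at least one true predictor was kept in 63 to 80% at 80% success and 78 to 89% at 50%. Likely instability is what can be claimed.
- **Variable selection causes the extreme probabilities.** It does not. The full model is already overfitted, and in every N = 50 setting with four or more candidates selection moved the slope slightly towards 1. Deleting the selection sentence alone would not cure the problem. As sequenced, selection also comes after the cut-off and predictive values, so it does not alter them.
- **The model is unpenalised.** The plan does not say. Ordinary maximum likelihood is the natural reading, but it is an inference.
- **About 10 failures are expected.** That rate is borrowed from a series with a different outcome definition and mostly block-positive patients. Here everyone is operated on and four criteria must be met, so a balanced outcome is possible.
- **The protocol contradicts itself outright.** Its remark about earlier series also concerns subgroup analysis. Of the 100 patients in one series only 51 + 9 = 60 were operated on. For the other, "The authors reviewed 101 patients all, which underwent cervical or lumbar decompression". Both operated groups still exceed 50, so the tension is real, but the questions are not identical.
- **Fixing two predictors, VAS change and walk time, is the obvious cure.** When other measures are the true predictors, that pair discriminates worse than selection at p<0.157 (AUC 0.61 to 0.64 against 0.66 to 0.68). It would also demote duration of relief, which Aim 2 names.

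Pilot status lowers the consequence. It does not remove it, because the threshold work is meant to inform the larger study.

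**Conclusion.** The concern holds as a missing safeguard. If the combined model is fitted by ordinary maximum likelihood to about five or more of the collected measures in 50 patients, its probabilities will typically be too extreme, before and after selection, and cannot be taken at face value as likelihoods. The direction is robust: the median slope was below 1 in every N = 50 setting examined. The size is not fixed by the documents. It rests on assumed odds ratios, correlations, candidate counts and success rates, with five candidates giving about 0.4 to 0.6 for the full model and 0.5 to 0.65 after selection. Instability of the selected set is likely but conditional on those inputs, with exact recovery of 3 to 16% in the five-candidate case and good recovery in the favourable cases shown. The plan should be changed, but the point does not invalidate the study.

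**What to change.** In the Statistical Analysis section:

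1. Name a short list of response measures in advance, including duration of relief so that Aim 2 is served, and fit the combined logistic model with a ridge penalty chosen by cross-validation.
2. Set the model cut-off and the positive and negative predictive values on that penalised model.
3. Replace the variable-selection sentence. State that any simplified model is exploratory, is reported with bootstrap selection frequencies and optimism-corrected performance (each resample repeating the whole procedure, including the choice of penalty and of cut-off), and will not be used to decide which aspects of the response matter.

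The cost is wording, standard software and a little more analysis time. Visits, enrolment and care do not change. Odds ratios will be slightly shrunken, and mild over-shrinkage is possible (slope about 1.1 to 1.3 with five candidates). The penalty corrects the probability scale; it does not make choosing predictors from 50 patients reliable, which is why the third step is needed.
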